9.2.1.1. Suspected Unexpected Serious Adverse Reactions

Suspected unexpected serious adverse reactions (SUSARs) are serious events that are not listed in the IB and that the investigator identifies as related to investigational product or procedure. US 21 CFR 312.32 and EU Clinical Trial Directive 2001/20/EC and the associated detailed guidances or national regulatory requirements in participating countries require the reporting of

SUSARs. Lilly has procedures that will be followed for the recording and expedited reporting of SUSARs that are consistent with global regulations and the associated detailed guidances.

9.2.2. Complaint Handling

Lilly collects product complaints on investigational products and drug delivery systems used in clinical trials in order to ensure the safety of study participants, to monitor quality, and to facilitate process and product improvements.

Patients should be instructed to contact the investigator as soon as possible if he or she has a complaint or problem with the investigational product so that the situation can be assessed.

9.3. Treatment of Overdose

Excess insulin administration may cause hypoglycemia. For the purposes of this study, an overdose of LY900014 is considered any dose higher than the calculated individualized dose to cover the carbohydrate content of meals consumed during the study.

Mild episodes of hypoglycemia usually can be treated with oral glucose. Adjustments in drug dosage, meal patterns, or exercise may be needed. More severe episodes with coma, seizure, or neurologic impairment may be treated with intramuscular/SC glucagon or concentrated IV glucose. Sustained carbohydrate intake and observation may be necessary because hypoglycemia may recur after apparent clinical recovery.

Refer to the IB for LY900014 and the package insert for insulin lispro (Humalog package insert 2015).

9.4. Safety

9.4.1. Laboratory Tests

For each patient, laboratory tests detailed in [Appendix 2](#) should be conducted according to the Schedule of Activities (Section 2).

Blood and urine samples will be collected to determine whether patients meet inclusion/exclusion criteria and to monitor patient health. Routine clinical laboratory tests will be analyzed by a local laboratory.

9.4.2. Vital Signs

For each patient, vital signs measurements should be conducted according to the Schedule of Activities (Section 2) and as clinically indicated.

Blood pressure and pulse rate should be measured after at least 5 minutes supine.

If orthostatic measurements are required, patients should be supine for at least 5 minutes and stand for at least 2 minutes.

If the patient feels unable to stand, supine vital signs only will be recorded.

Unscheduled orthostatic vital signs should be assessed, if possible, during any AE of dizziness or posture-induced symptoms. Additional vital signs may be measured during each study period if warranted and agreed upon between the sponsor and investigator.

Body temperature will be measured as specified in the Schedule of Activities (Section 2) and as clinically indicated.

9.4.3. Physical Examination

Physical examinations and routine medical assessments will be conducted as specified in the Schedule of Activities (Section 2) and as clinically indicated.

9.4.4. Body Weight

Body weight will be recorded as specified in the Schedule of Activities (Section 2) and as clinically indicated.

9.4.5. Electrocardiograms

For each patient, single 12-lead digital ECGs will be collected according to the Schedule of Activities (Section 2). ECGs must be recorded before collecting any blood for safety or PK tests. Patients must be supine for approximately 5 to 10 minutes before ECG collection and remain supine but awake during ECG collection. ECGs may be obtained at additional times when deemed clinically necessary. All ECGs recorded should be stored at the investigational site.

ECGs will be interpreted by a qualified physician (the investigator or qualified designee) at the site as soon after the time of ECG collection as possible and ideally while the patient is still present to determine whether the patient meets entry criteria at the relevant visit(s) and for immediate patient management, should any clinically relevant findings be identified.

If a clinically significant finding is identified (including, but not limited to, changes in QT/QT corrected for heart rate [QTc] interval from baseline) after enrollment, the investigator will determine if the patient can continue in the study. The investigator or qualified designee is responsible for determining if any change in patient management is needed and must document his/her review of the ECG printed at the time of collection. Any new clinically relevant finding should be reported as an AE.

9.4.6. Plasma Glucose Monitoring

The patient's plasma glucose concentrations will be monitored frequently at the times specified in the Schedule of Activities (Section 2) using a **CCI** available at the site for safety assessments.

Additionally, patients will be instructed to conduct daily self-plasma glucose monitoring at a minimum of 4 time points (premeals: breakfast, lunch, dinner; and bedtime) during the outpatient phase of the study. Patients will be instructed to immediately report any episodes of hyperglycemia or hypoglycemia requiring an adaptation of the treatment regimen to the investigator, who will be responsible for advising the patient on what further actions to take.

Patients will be instructed to record the date, time, and result of each self-plasma glucose monitoring test. Additional monitoring may be requested at the investigator's discretion.

Hypoglycemic episodes will be defined as clinical events with or without symptoms typical of hypoglycemia, accompanied by a plasma glucose level of ≤ 70 mg/dL (3.9 mM), which are reversed by oral carbohydrates or IV glucose. These episodes will be captured in the CRF. In addition, episodes that fulfill the criteria of severe hypoglycemia as defined in Section 9.4.9.1 will be reported as an SAE. Investigator review of glucose results clinically indicative of hypoglycemia will be required.

Hypoglycemia is considered a therapeutic effect of insulin lispro and will generally not be considered a clinically significant drug-related AE but will be treated appropriately. Additional monitoring of plasma glucose levels may be performed at the discretion of the investigator.

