5.1.1. Inpatient Procedures

Patients will arrive at the CRU in the early evening of Day -1 (approximately 5:00 PM), and a CGM system will be inserted before the start of a standardized dinner (at approximately 7:00 PM). A standard system will be used for CGM (for example, CCI [REDACTED]). The patients will wear this device during all inpatient days. The CGM device will be calibrated using the plasma glucose values obtained with the CCI [REDACTED] by site personnel. Regular monitoring of blood glucose using the CCI [REDACTED] (approximately every 2 hours) will be performed during the complete inpatient period outside of the breakfast meal test procedures.

The catheter needle will be inserted during the evening of Day -1 and should stay at the same catheter insertion-site location for the duration of each period (3 days). If the patient needs to change the catheter during the study period (between Day 1 to Day 3), the patient may repeat that study period once only if the maximum blood loss over the entire study (that is, the blood loss during the past periods and the expected blood loss of upcoming periods) will not exceed approximately 550 mL. The patient will not be withdrawn from the study even if the period cannot be repeated.

A breakfast MMTT of fixed nutrient composition will be administered on Day 1 and Day 3, and a high-glycemic index breakfast test meal will be administered on Day 2 for each of the 4 treatment periods. Additionally, a standardized lunch will be administered on Days 1, 2, and 3, and a standardized dinner will be administered on Days 1 and 2. A detailed description of the test meals is presented in Section 6.3.1. Patients will be without further oral food intake from the start of each meal to completion of blood collection for the breakfast meals and to 5 hours after the start of the meal for the lunch and dinner meals (approximately 300 minutes) unless required to treat hypoglycemia, as defined by a plasma glucose level <56 mg/dL (3.1 mM) or symptoms that require treatment as assessed by the investigator during the inpatient period that is reversed with either rapidly absorbable oral carbohydrates or IV glucose. If a patient's plasma glucose concentration rises above 306 mg/dL (17 mM) for more than 1 hour, insulin glulisine (CCI [REDACTED]) will be administered IV. In both cases, blood samples for plasma glucose (for safety) will be taken, and PK samples will be collected as planned.

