7.1.2. Noninvestigational Medicinal Products

For daily dosing during the 1-week lead-in period and between study periods, patients will be provided with commercially available Humalog 10-mL vials for infusion; in these situations, Humalog will be considered as a noninvestigational medicinal product for study procedures. Commercially available CCI and 20% dextrose will be used for the 7-hour run-in period before the start of the MMTTs on Days 1 and 3 and can be used up to approximately 6 hours before the start of the Day 2 breakfast test meal. In addition, if a patient's plasma glucose concentration rises above 306 mg/dL (17 mM) for more than 1 hour during the meal test, CCI will be administered. Apidra or IV glucose can also be administered during the complete inpatient period outside of the test meal procedures if required to treat hypo- or hyperglycemia at the discretion of the investigator.

The doses of Humalog, CCI, and glucose administered during the trial must be recorded in the CRF.

Humalog used as a noninvestigational medicinal product will be supplied by the sponsor. All other noninvestigational medicinal products will be sourced locally by the site and will be used from their original packaging.

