9.4.9.1. Glucose Monitoring

Hypoglycemia will be described using the following definitions:

- Documented hypoglycemia:
 - **Symptomatic hypoglycemia:** an event during which typical symptoms of hypoglycemia are accompanied by plasma glucose ≤ 70 mg/dL (3.9 mM)
 - **Asymptomatic hypoglycemia:** an event not accompanied by typical symptoms of hypoglycemia but with plasma glucose ≤ 70 mg/dL (3.9 mM)

- **Unspecified hypoglycemia:** an event during which plasma glucose ≤ 70 mg/dL (3.9 mM) but no information relative to symptoms of hypoglycemia was recorded
- **Probable symptomatic hypoglycemia:** an event during which symptoms indicative of hypoglycemia are not accompanied by a plasma glucose determination (but that was presumably caused by plasma glucose ≤ 70 mg/dL [3.9 mM])
- **Severe hypoglycemia:** an event requiring assistance of another person to actively administer carbohydrate, glucagon, or other resuscitative actions. During these episodes, the subject has an altered mental status and cannot assist in their own care, is semiconscious or unconscious, or experienced coma with or without seizures and may require parenteral therapy. Plasma glucose measurements may not be available during such an event, but neurological recovery attributable to the restoration of blood glucose concentration to normal is considered sufficient evidence that the event was induced by a low plasma glucose concentration (≤ 70 mg/dL [3.9 mM])
- **Nocturnal hypoglycemia:** any hypoglycemic event (documented symptomatic, asymptomatic, probable symptomatic, or severe hypoglycemia) that occurs between bedtime and waking
- **Relative hypoglycemia:** an event during which typical symptoms of hypoglycemia, that do not require the assistance of another person, are accompanied by plasma glucose > 70 mg/dL (3.9 mM), but these levels may be quickly approaching the 70-mg/dL (3.9 mM) threshold
- **Total hypoglycemia:** an optional category that combines all cases of hypoglycemia. If an event which hypoglycemia falls into multiple subcategories, the event is only counted once in this category

Investigator review of documented glucose results in the diary or during the inpatient period that are clinically indicative of hypoglycemia will be required.

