9.5.7 Blood glucose monitoring and Hypoglycemia

Hypoglycemic events will be appropriately recorded in the CRF. In the case of a hypoglycemic event, the actual blood glucose value, if measured, will be recorded in the CRF, together with any treatments administered, and the time of occurrence relative to the patient's last meal. Each category of hypoglycemic events (defined below) will be listed and summarized for the outpatient, inpatient before the MMTT, inpatient during the MMTT, or inpatient after the MMTT periods and overall. Severe hypoglycemic events will be reported as SAEs. "During MMTT" refers to 0-300 minutes postdose. Events will be summarized by treatment, bolus dose administration method and meal.

Hypoglycemia is defined as follows:

- Documented Hypoglycemia:
 - Symptomatic hypoglycemia: An event during which typical symptoms of hypoglycemia are accompanied by plasma glucose ≤ 70 mg/dL (≤ 3.9 mmol/L)
 - Asymptomatic hypoglycemia: An event not accompanied by typical symptoms of hypoglycemia but with plasma glucose ≤ 70 mg/dL (≤ 3.9 mmol/L)
- Unspecified hypoglycemia: An event during which plasma glucose ≤ 70 mg/dL (≤ 3.9 mmol/L) but no information relative to symptoms of hypoglycemia was recorded.
- Probable symptomatic hypoglycemia: An event during which symptoms indicative of hypoglycemia are not accompanied by a plasma glucose determination (but that was presumably caused by PG ≤ 70 mg/dL [≤ 3.9 mmol/L]).
- Severe hypoglycemia: An event requiring assistance of another person to actively administer carbohydrate, glucagon, or other resuscitative actions.

- Nocturnal hypoglycemia: Any hypoglycemic event (documented symptomatic, asymptomatic, probable symptomatic, or severe hypoglycemia) that occurs between bedtime and waking
- Relative hypoglycemia: an event during which typical symptoms of hypoglycemia, that do not require the assistance of another person, are accompanied by plasma glucose >70 mg/dL (3.9 mmol/L), but these levels may be quickly approaching the 70 mg/dL (3.9 mmol/L) threshold
- Total hypoglycemia: an optional category that combines all cases of hypoglycemia. If an event which hypoglycemia falls into multiple subcategories, the event is only counted once in this category

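### Protocol 9.4.6 makes reversal by carbohydrate or IV glucose part of a recordable hypoglycemic episode; 9.4.9.1 and SAP 9.5.7 do not, so untreated values of 56–70 mg/dL after meals may be under-recorded

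*Protocol*

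**What the plan says.** **Recording definition (Protocol 9.4.6).** Symptoms are not required: "Hypoglycemic episodes will be defined as clinical events with or without symptoms typical of hypoglycemia". The definition then adds glucose at or below 70 mg/dL and one further element: "which are reversed by oral carbohydrates or IV glucose. These episodes will be captured in the CRF".

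**Classification (Protocol 9.4.9.1).** Asymptomatic hypoglycemia is "an event not accompanied by typical symptoms of hypoglycemia but with plasma glucose ≤ 70 mg/dL (3.9 mM"). Symptomatic and unspecified events use the same cut-off. None of the three mentions treatment or reversal.

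**Analysis (SAP 9.5.7).** The same categories are repeated without a reversal condition. On the data source the SAP says "Hypoglycemic events will be appropriately recorded in the CRF", and it lists any treatment given among the items recorded. Each category is summarized for several periods, one of them the meal test (0–300 minutes postdose), by treatment, bolus mode and meal.

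**Food in the post-meal windows (Protocol 5.1.1).** Patients take no further food for about 300 minutes after each meal, with this exception: "unless required to treat hypoglycemia, as defined by a plasma glucose level <56 mg/dL (3.1 mM) or symptoms". The symptom limb covers only those the investigator judges to need treatment. Protocol 7.1.2 adds discretionary treatment at other times: "IV glucose can also be administered during the complete inpatient period outside of the test meal procedures".

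**The concern.** The definition that governs recording is narrower than the categories it has to feed. In most settings this might matter little, because a low value would often be treated and so meet the reversal clause. In the post-meal windows the protocol itself makes treatment of a value between 56 and 70 mg/dL the exception, so the clause matters most there.

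Frequency and/or severity of hypoglycemia is a listed endpoint of the safety objective (Protocol Table ITSC.4.1), and Protocol 3.2 names less late postprandial hypoglycemia as a possible benefit of a faster insulin. If a site follows 9.4.6 literally, the asymptomatic, documented and overall counts for the meal test would be too low, in the window where glucose is sampled most closely. Because recording would depend on treatment, any undercount could differ between products whose lows differ in depth or symptoms.

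**Working it through.** The plan states no figure for this point, so the check sets the sections side by side, then makes a unit check and a count of the data available.

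**1. Is the 56–70 mg/dL band real or a conversion slip?** Dividing mg/dL by 18.016: 56 / 18.016 = 3.11 mM and 70 / 18.016 = 3.89 mM. These agree with the stated 3.1 and 3.9 mM. The two thresholds do differ.

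**2. Each kind of low value in a post-meal window, under each rule.**

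| Value | Food exception in 5.1.1 | Meets 9.4.6 as written | Event under 9.4.9.1 and SAP 9.5.7 |
|---|---|---|---|
| Below 56 mg/dL | applies | yes, once reversed | yes |
| 56–70 mg/dL, symptoms judged to need treatment | applies | yes, once reversed | yes |
| 56–70 mg/dL, symptoms judged not to need treatment | does not apply | no, if untreated | yes |
| 56–70 mg/dL, no symptoms | does not apply | no, if untreated | yes |

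The last two rows are the mismatch. A patient at 62 mg/dL without symptoms is an example.

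**3. Does another section close the gap?**
- 9.4.6 and 9.4.9.1 both require investigator review of results clinically indicative of hypoglycemia. Neither says that an untreated low then becomes a CRF event.
- SAP section 3 says the SAP supersedes the protocol's statistical considerations. That does not reach the site's recording instructions.
- The glucodynamic parameters in SAP 9.4.1 are glucose AUCs and maximum changes from baseline. None counts low values.
- SAP 9.5.10 derives CGM time at or below 70 mg/dL without a treatment condition, by meal. The outcome variables come from the lunch and dinner data, so the breakfast tests are not clearly covered.
- Neither document has a rule that turns the serial plasma glucose values into hypoglycemic events.

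**4. What is measured regardless of the event form?** The Schedule of Activities lists 24 plasma glucose times per breakfast test. Two of them (−30 and −15 minutes) precede the dose, so 24 − 2 = 22 lie at 0–300 minutes. Gaps are at most 15 minutes up to 240 minutes, with one last sample at 300.
- Tests per completer: 3 days × 4 periods = 12.
- Tests in 20 completers: 12 × 20 = 240.
- Values per completer: 22 × 12 = 264.
- Values in 20 completers: 22 × 240 = 5,280.

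These are upper limits. Protocol 5.1.1.3 drops the Day 2 test if glucose or insulin was needed in the preceding 6 hours. With no Day 2 tests at all, 2 × 4 × 20 = 160 tests would remain. The counts describe the opportunity to observe events. They are not an estimate of how many are missed.

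**The case against.** The strongest reply is that this is a drafting inconsistency with no demonstrated loss of data. A reader might infer that untreated lows are excluded from the CRF, but 9.4.6 says only that the episodes it defines are captured. It does not say that others are not. An asymptomatic category in both documents, and treatment listed as a data item in SAP 9.5.7, suggest that untreated events are expected on the form. The CRF completion guidelines mentioned in Protocol 7.6 may settle the matter and are not available here. This stands, and it limits the conclusion to ambiguity and possible under-recording.

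A reader might also infer that the protocol orders treatment withheld until glucose falls below 56 mg/dL. It does not say so: 5.1.1 restricts food and names an exception, part of which rests on the investigator's judgment. This stands too.

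Third, the values exist. Protocol 9.6.2 uses the meal-test glucose for safety management and glucodynamics, SAP 9.1 lists all databased data, and lunch and dinner lows are partly covered by CGM time at or below 70 mg/dL. This makes the gap recoverable. It does not supply the missing rule, and time in range is not an event count.

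Fourth, the objective is exploratory, SAP 9.5.7 is descriptive, and the same recording rule applies to both products in a patient- and investigator-blind crossover. A bias between products is possible, but nothing in the documents shows one.

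**Conclusion.** The inconsistency is real. By its wording, 9.4.6 makes reversal part of what is recordable, while 9.4.9.1 and SAP 9.5.7 do not. Combined with the food exception in 5.1.1, untreated values of 56–70 mg/dL after meals, asymptomatic or with symptoms judged not to need treatment, fail the 9.4.6 definition although the SAP would count them. They may be under-recorded in the meal-test summaries.

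The size is unknown. The documents give no frequency for such values and no basis for a direction by product. Up to 22 plasma glucose values in each of up to 240 breakfast tests would allow the events to be identified, if a rule were stated. The SAP category below 54 mg/dL should be little affected, since it lies below the 56 mg/dL exception.

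The conclusion assumes that sites work from the text of 9.4.6 and that the CRF guidelines do not already override it. It does not support a claim that the events are lost or that the product comparison is biased. Correction is worthwhile because the endpoint is stated and the remedy is cheap.

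**What to change.** 1. In Protocol 9.4.6, remove reversal by carbohydrate or IV glucose from the definition of a recordable episode, so that it agrees with 9.4.9.1 and SAP 9.5.7. Keep any treatment given as a recorded item.
2. In SAP 9.5.7, state that documented inpatient hypoglycemia is also identified from all recorded plasma glucose values at or below 70 mg/dL, whether or not treated, and merged with the CRF symptom data.
3. Prespecify how consecutive low values form one event. The rule should cover the single 60-minute gap between the 240- and 300-minute samples.
4. Check that the CRF completion guidelines say the same.

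The cost is one clause, a small derivation from data already collected, and more asymptomatic events in the tables. No extra samples are needed. The passages need reconciling only on what counts as a recordable event. No view is taken on the treatment threshold in 5.1.1.

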9.4.7. Catheter Insertion-Site Assessments

Catheter insertion-site assessments, including inspection of the site for signs such as edema, erythema, and rash, will be conducted as specified in the Schedule of Activities (Section 2) and as clinically indicated.

9.4.7.1. Subjective Procedure: Examination of Infusion Set and Catheter

When the infusion set and reservoir are changed (except for Period 1, Day -1) at the site, a macroscopic (visual) and microscopic examination (ideally immediately after removing the catheter, but no longer than 120 minutes) will be performed including the following:

- a check on the infusion set or the catheter for signs of kinking or other damage. In case of damage, the damage should be described in the CRF and photographic evidence should be taken
- a check of the insulin in the reservoir and infusion-set tubing for color change and crystals and/or particles including the location of these (that is, reservoir, infusion set)
- a microscopic check of the catheter tubing to exclude micro-occlusions and/or particles in the tubing

